55-74). There were 297 individuals who were reachable and 54 of these were eligible for LCS according to the USPSTF criteria. We were able to contact a higher proportion of current smokers (47%) than former smokers (30%). Eligibility was higher in current smokers (28%) versus former smokers (11%). Also, of the 54 total eligible, 28 enrolled. Despite these small numbers, we were able to show the DCP participation was associated with LDCT completion at 90 days ($p=0.03$).

Study Design We propose a 1 year project including a **6 month intervention** period. This study will be a cohort with comparison to usual care in other practices in the same health system using propensity-matching methodology. **Study population/eligibility** Inclusion/exclusion criteria will be based on the USPSTF and CMS lung cancer screening guidelines: age 55- 80, with a 30 pack year smoking history, no symptoms consistent with cancer, and no CT scan of the lungs within the last year. Physicians will be given the chance to eliminate participants based on limited life expectancy or prohibitive comorbid conditions. Case finding in our prior work was difficult and recruiting active smokers has a higher yield. Prior work indicated that this pool yielded a higher proportion of truly eligible, reachable individuals. Plus, we want to test the feasibility of a more intense smoking cessation intervention. To address recruitment barriers, we will work with practices and PCPs to promote as a study “conducted with the PCP,” including the physician name or practice name when possible on recruitment materials e.g. written letters and email cosigned by their PCP. To address case finding barriers, we will allow patients to easily opt out of future contact via mail, email or phone. We will work with our advisory panel to explore other methods to enhance recruitment and case-finding such as using the secure EMR portal to screen for LCS eligibility and/or updating smoking history. Finally, we have added \$50 patient incentives per patient for participation.

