Data Acquisition Following approval by the CCHS Institutional Review board, lists of potentially eligible individuals from participating and non-participating practices will be obtained from EMR data. These lists will be automatically entered into a REDCap® for CONSORT tracking. Lists will be organized according to PCP whom will be given 7 working days to review lists and eliminate any patient they feel would not be appropriate for this study. Remaining potentially eligible patients will receive a letter, cosigned by their personal physician which introduces the study and offers the opportunity to easily opt out of further contact. After an opt-out period of 7 working days, patients will be contacted, screened for eligibility and invited to participate. After formal consent, we will collect demographics, socioeconomic variables and smoking history. Baseline data will be collected regarding knowledge, preference and decisional conflict related to lung cancer screening. Standard patient education materials will be sent to patients. The DCP session will be conducted within 30 days of enrollment. A follow up telephone call will occur within 30 days of DCP completion, and will include items to assess patient perception of the process, knowledge about lung cancer screening and decisional conflict (Appendix 3) related to lung cancer screening (10). At 60 days after the decision counseling session, patient charts/electronic medical record data will be audited for the primary outcome, LDCT scan report. Prior work showed the average time from DCP to LDCT was ≤ 60 days. Intermediate (process) outcomes in EMR include lung cancer screening discussion, referral/order for LDCT, or referral to the CCHS LHSP. Eligible patients in the usual care group (in the non-participating clinics) will be identified electronically as stated above and LDCT screening assessed in a 60 day study period from their most recent office visit. Information available in EMR for all patients including controls and individuals who are “unreachable” comprises gender, age, race, ethnicity, insurance status, marital status, smoking status, comorbidities, such as COPD, Heart disease, diabetes, hypertension and zip code (surrogate for socioeconomic status). Information collected from individuals who are reached but ineligible will include all of the above plus smoking status, pack years, and reason for ineligibility. Information collected from individuals who decline participation will include all of the above plus reason for declining participation.

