
Statistical analysis

Aim 1 Compare low dose CT scan completion in the DCP cohort of current smokers versus usual care propensity-matched controls at 60 days. *Hypothesis: Participation in the DCP will be associated increased participation in LDCT, compared with both eligible enrollees who do not participate and with eligible patients in usual care practices.* Demographic and clinical variables of the intervention and control groups will be compared using T-Test, Wilcoxon-Rank sum test and chi-squares. We will conduct a 1-to-1 propensity score matching to compare the proportion of patients who screen between the groups. We will use a logistic regression model to build propensity scores to match patients in the intervention and control groups. We will model the probability of being in the intervention group using all the patients level variables extracted from the medical records as listed above. Whether they are in a participating practice or not will not be included in the model as an independent variable. The nearest neighborhood method without replacement will be used for matching. We will set the caliper width according to the standard deviation for the propensity score. Each control will be assigned a probability score and matched with a patient in the intervention group. In a second step, we will compare the characteristics of the patients and chosen controls to verify that they are very similar. We will use a simple chi-square to compare the percentage of patients in the control and intervention groups who complete the LDCT scan within 60 days.

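### Patients with an LDCT order or LHSP referral already open before the study starts are neither excluded nor matched on, so scans already under way count as 60-day uptake in either group

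*Combined protocol and SAP*

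**What the plan says.** All references are to the combined protocol and SAP.

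- **Study population/eligibility.** The imaging criterion is "no CT scan of the lungs within the last year". Nothing is said about orders or referrals not yet acted on. Physician removal has stated grounds: "Physicians will be given the chance to eliminate participants based on limited life expectancy or prohibitive comorbid conditions".
- **Data Acquisition, list review.** The wording here is wider: physicians may "eliminate any patient they feel would not be appropriate for this study". No rule on pending orders is given.
- **Data Acquisition, DCP outcome.** At 60 days after the session, "patient charts/electronic medical record data will be audited for the primary outcome, LDCT scan report". The session itself may come later than consent: "The DCP session will be conducted within 30 days of enrollment". No start date for counting scans is stated.
- **Data Acquisition, usual-care outcome.** Controls have "LDCT screening assessed in a 60 day study period from their most recent office visit".
- **Data Acquisition, process outcomes.** These include "referral/order for LDCT, or referral to the CCHS LHSP". Orders and referrals appear here only, as outcomes. They are absent from the list of EMR items available for all patients including controls.
- **Statistical analysis, Aim 1.** The propensity model uses the EMR variables listed earlier. The primary test is a chi-square on the percentage "who complete the LDCT scan within 60 days".

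**The concern.** A patient with an open order and no scan passes the eligibility rule, because that rule looks only at completed imaging. If the scan takes place in the window, the patient is a success, although the order predates the DCP contact or the index visit. Neither group's outcome definition requires the order to follow time zero.

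Matching is the only control for confounding in Aim 1, and it cannot balance a variable it does not contain. This variable is likely to be strongly prognostic: the Innovation section itself names physician recommendation as among the strongest predictors of screening, and an open order is the recorded form of that recommendation. The two groups also arise differently. Enrollees agree to take part after a letter cosigned by their physician and receive $50, whereas controls are found electronically and are never approached. There is no reason to expect equal shares of open orders, and nothing in the plan would reveal unequal ones.

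**Working it through.** **Inputs.** From the power calculation: 15% usual care, 45% DCP, 40 per group, 85% power, with 20 points as the smaller target difference. From Specific Aims: 100 enrollees. Alpha and sidedness are not stated; two-sided 0.05 is assumed. Assumed because the documents give nothing: the share with an open order (q), and their scan rate within 60 days regardless of the DCP (s).

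**The plan's own figure.** Power for 15% v 45% with 40 per group, by the pooled normal approximation without continuity correction, is 84.7%. The stated 85% is reproduced, and the present point does not dispute it.

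**Model.** With p the scan rate among patients without an open order, a group's rate is q·s + (1 − q)·p. With no DCP effect, the spurious difference is

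(q_DCP − q_control) × (s − p).

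The term s − p matters: patients with open orders would otherwise be scanned at the background rate, not at zero.

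**Unequal shares, p = 15%.**

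| q DCP v control | s | Calculation | Spurious difference |
|---|---|---|---|
| 6% v 3% | 50% | 0.03 × 0.35 | 1.05 points |
| 10% v 4% | 60% | 0.06 × 0.45 | 2.7 points |
| 15% v 5% | 60% | 0.10 × 0.45 | 4.5 points |

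Check of the middle row: DCP 0.10 × 0.60 + 0.90 × 0.15 = 19.5%; control 0.04 × 0.60 + 0.96 × 0.15 = 16.8%; difference 2.7 points. Reversing the shares gives −2.7.

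If the 15% already includes control patients with open orders, then p = (0.15 − 0.04 × 0.60)/0.96 = 13.1% and the middle row becomes 0.06 × (0.60 − 0.131) = 2.8 points, so that choice hardly matters.

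**Effect on the test.** In a deliberately sharp case, 10% v 0% with s from 50% to 90% and no DCP effect, the spurious difference is 0.10 × (0.50 − 0.15) = 3.5 to 0.10 × (0.90 − 0.15) = 7.5 points. The nominal 5% rejection rate becomes 7.0% to 13.7% at 40 per group and 10.1% to 27.3% at 100 per group.

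**Equal shares.** There is no false difference and rejection stays at 5%. If open-order patients scan at s in both groups, a 30-point effect shrinks to (1 − q) × 30: 27 points at q = 10%. Power at 40 per group then falls to 71.9% to 74.4% for s from 90% to 50%.

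**Cost of exclusion.** From 100 pairs, setting aside 5%, 10% or 20% leaves 95, 90 or 80, with power for 15% v 35% of 89.6%, 87.9% or 83.8%.

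**The case against.** Four objections carry weight.

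1. **Direction.** A reader might infer that the gap favours the DCP, on the view that people just told to get a scan are keener to join. The documents do not show this. The intervention is aimed partly at patients unaware that they are eligible, and someone with a scan already ordered may see no use in decision counseling. Physicians could also strike such patients at list review. That review is the nearest safeguard, but it is discretionary and its stated grounds are prognosis and comorbidity, so it narrows the gap without closing it.
2. **Causation.** A reader might infer that the DCP could not have caused any scan ordered earlier. That goes too far. The outcome is completion, and counseling that clarifies preference could change whether an open order is completed, either way. What stands is that the plan cannot separate such scans from newly prompted ones.
3. **Size.** Multiplying the difference in shares by the scan rate alone gives 0.06 × 0.60 = 3.6 points for the middle case. This ignores the 15% background rate; the figure is 2.7.
4. **Data.** A reader might infer that order dates are already being extracted in both groups. The text lists orders and referrals as process outcomes, mentions no dates, and does not say that they are collected for controls.

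It is also fair to say that this is a non-randomized pilot with other unmeasured differences between volunteers and unapproached controls. But this difference can be measured, and cheaply.

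**Conclusion.** The gap is real. No rule excludes, dates or balances LDCT orders or LHSP referrals that predate time zero, and resulting scans count as uptake in an unadjusted comparison. The size is unknown. Under the stated assumptions it is about 2.7 points, range about 1 to 4.5, which is modest beside a target of 20 or 30 points but not negligible for a test that relies on matching alone. The sign depends on which group holds more open orders, and with equal shares the effect is dilution only. The documents support neither a claim that the DCP effect is necessarily overstated nor one that the planned comparison is invalid. They support the conclusion that the estimate cannot be read cleanly without this variable. The plan should be changed on this point.

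**What to change.** From the EMR, in both groups, flag any LDCT order or LHSP referral that was open and unscanned before the patient's time zero:

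- **DCP patients:** open before the list pull or first study contact, with one of these fixed in advance. The session date is too late, because the letter, call and education materials come first and an order placed after them may be a study effect.
- **Controls:** dated before the index office visit. Orders written at that visit are genuine usual-care uptake and stay in.

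One list-pull cut-off for both groups would be simpler but could itself favour the DCP. As an assumed illustration, if 8% of controls had an index-visit order still open at the pull and 60% of these were scanned, removing them would lower a 15% control rate to (0.15 − 0.08 × 0.60)/0.92 = 11.1%. That is a spurious gain of 3.9 points, more than the 2.7 to be removed.

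Exclude flagged patients from the Aim 1 primary comparison before matching, tabulate their number and scan rate by group, and report a sensitivity analysis that keeps them with the flag in the propensity model.

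The cost is one dated EMR pull in both groups, which the plan does not yet specify, and a few patients lost from Aim 1. At 100 matched pairs, setting aside 10% leaves about 88% power for 15% v 35%. At the minimum of 40 per group it would leave 36 and 80.7% power for 15% v 45%, so the exclusion is affordable provided that enrollment is near plan.

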Intervention The DCP is an online software application that supports an interactive session that focuses on patient education and preference clarification. Patients will be contacted by phone or other methods to provide information about the study, be invited to participate, consented, and then scheduled for decision counseling. Neither the DCP tool nor this process is directive; the DCP session does not push the patient to screen but, rather, clarifies the patient's current preference (screen or not) and identifies key reasons for that preference. In the session, the decision counselor and patient will review the options, (to screen or not to screen for lung cancer) using publicly available patient education materials (Appendices 1 & 2) (8, 9). Then, the decision counselor will guide the patient through 5 steps: 1) identify factors most likely to influence the decision to screen 2) assign importance (decision weight) to the factors 3) compare the relative weight of the most important factors 4) generate a decision score, and 5) generate a personal summary form which can be made available in the EMR for physician review with the patient. Next steps will be tailored to each practice, and can include referral to PCP for further discussion and/or referral to the Lung Health Screening Program (LHSP). The decision counselor will be trained as a smoking cessation coach and as a “mini-expert” in system and community resources for smoking cessation.

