Power calculation based on primary outcome: According to our preliminary study, 45% of those who complete the DCP decided to screen for lung cancer whereas the know rate of screening among patients in usual care is 15%, which makes a difference of 30%. A sample size of 40 patients in each group will achieve 85% power to detect a difference between the group proportions of 30%. The proportion in the intervention group is assumed to be 15% under the null hypothesis and 45% under the alternative hypothesis. To detect a difference of 20%, we will need a sample size of 60 patients in each group to achieve a power of 80%. We expect that 2000 patients will be identified as potentially eligible for the study in the EMR and 1000 will be reachable. Of those 300 (30%) will be confirmed eligible during the phone call and 150 (50%) will accept to participate in the DCP. We will therefore have ample power to detect a difference as small as 20% between our 2 groups.

Aim 2 Compare the characteristics of the patients not recruited in the study to the characteristics of those who accepted to enroll. *Hypothesis: Patients recruited to the study versus those who are not will be different demographically and geographically.* We will use descriptive statistics to examine the characteristics of the patients of the intervention practices who were eligible but could not be reached and of the patients who were reached but refused to be in the study. We will also compare the characteristics of these patients to those of the patients who enrolled in the study. We will use logistic regression models to determine which independent characteristics are associated with agreeing to be in the study.

Aim 3 Test the feasibility of intensive smoking cessation as part of the DCP. *This aim is hypothesis generating.* At 30 days, we will ask patients about participation in smoking cessation, quit attempts and for general comments on their needs and satisfaction with our smoking cessation efforts. We will explore trends associated with these intermediate outcomes related to cessation including engaging in cessation and quit attempts. We will illicit qualitative information from participants about how to make this part of the program useful and patient-centered.

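### Aim 1 compares consenting DCP volunteers with electronically identified controls; matching on EMR variables cannot remove volunteer selection, and no planned analysis checks for it.

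*Combined protocol and SAP*

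**What the plan says.** **DCP group.** Under Data Acquisition, EMR lists go to the primary care physicians for review. Under Study Design, "Physicians will be given the chance to eliminate participants based on limited life expectancy or prohibitive comorbid conditions". Remaining patients get a letter and an opt-out period, and are then telephoned and screened for eligibility. The Intervention section says patients will "be invited to participate, consented, and then scheduled for decision counseling". Study Design adds $50 "patient incentives per patient for participation". The power paragraph expects that "2000 patients will be identified as potentially eligible for the study in the EMR and 1000 will be reachable", that 300 will be confirmed eligible, and that "150 (50%) will accept to participate in the DCP". In the preliminary study, "of the 54 total eligible, 28 enrolled".

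**Controls.** Data Acquisition says: "Eligible patients in the usual care group (in the non-participating clinics) will be identified electronically as stated above". Their LDCT is assessed over 60 days from the most recent office visit. For participants the chart audit is 60 days after the counseling session.

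**Matching.** Statistical analysis, Aim 1, builds the propensity score from the EMR variables listed under Data Acquisition ("Information available in EMR for all patients including controls and individuals who are" unreachable): gender, age, race, ethnicity, insurance, marital status, smoking status, comorbidities and zip code. Knowledge, preference and decisional conflict are collected after formal consent.

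**Non-participants.** The Aim 1 hypothesis names two comparators: eligible people who do not take part, and eligible patients in usual-care practices. The analysis text covers only the second. Aim 2 hypothesizes that recruits differ from non-recruits demographically and geographically.

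**The concern.** About half of the reached, eligible patients leave the DCP side by their own choice, and no such step is described on the control side. Someone who agrees to an hour with a lung-screening counselor may already be more inclined to have the scan. None of the matching variables measures that inclination. Preference, the one variable that comes close, does not exist for controls. The planned check that matched groups look alike will therefore not reveal the imbalance, and Aim 2 does not feed into Aim 1.

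The Aim 1 contrast then combines whatever DCP does with whatever volunteers would have done anyway. The Sustainability section presents this pilot as groundwork for a randomized trial, so an inflated difference could carry into that trial's sample size. The 45% used for power comes from pilot DCP completers and already carries the same selection.

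**Working it through.** **Inputs.** Usual-care rate 15%, DCP rate 45%, 40 per group for 85% power, 300 confirmed eligible, 150 accepting, 2000 listed (power paragraph); recruitment target 100 (Specific Aims). Alpha is not stated; I assume 5% two-sided. The ratio of screening in accepters to decliners is not in the documents and is varied as an assumption.

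**1. The plan's own figure.** For 45% v 15% with n = 40 per group, the pooled SE is √(2·0.30·0.70/40) = 0.1025 and the unpooled SE is √((0.45·0.55 + 0.15·0.85)/40) = 0.0968. Power = Φ[(0.30 − 1.96·0.1025)/0.0968] = Φ(1.02) ≈ 0.847. Exact enumeration of the uncorrected chi-square gives 0.852. The stated 85% reproduces.

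**2. Selection with no DCP effect.** Let q = 150/300 = 0.50 be the acceptance proportion, and hold the eligible population at 15%: q·r_acc + (1 − q)·r_dec = 0.15, so r_acc + r_dec = 0.30. Since r_dec cannot be negative, r_acc cannot exceed 30%. The planned test then compares r_acc with 15%. Exact two-sided probability of a significant result:

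| Ratio (assumed) | Accepters | Decliners | 100 pairs | 150 pairs |
|---|---|---|---|---|
| 1 (no selection) | 15% | 15% | 5% | 5% |
| 1.5 | 18% | 12% | 9% | 11% |
| 2 | 20% | 10% | 16% | 21% |
| 5 | 25% | 5% | 43% | 59% |
| limit | 30% | 0% | 73% | 88% |

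**3. Lower background.** Specific Aims cites 3.9% national screening in 2015. At that background a two-fold ratio (5.2% v 3.9%) gives 6% and 8%. The limit (7.8% v 3.9%) gives about 20% and 29%.

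**4. What the supportive analyses can show** (5% two-sided throughout).
- *Decliners v controls*, 300 − 150 = 150 decliners and 150 controls at 15%, same exact test: decliners at 12%, 10% or 5% are detected 12%, 26% or 84% of the time. Only strong selection would be found reliably.
- *Everyone listed*: 30 points × 150/2000 = 2.25 points. With 2000 per group (the control number is assumed), 17.25% v 15% gives Φ[(0.0225 − 1.96·0.01163)/0.01162] ≈ 0.49. At a 4% background, 6.25% v 4% gives Φ[(0.0225 − 1.96·0.00697)/0.00696] ≈ 0.90.
- *Accepters plus decliners*: if DCP adds 30 points and decliners screen at 15%, the rate is 0.5·45% + 0.5·15% = 30% v 15%, with 99% power at 300 per group. This group is still filtered on reach and phone-confirmed eligibility. If those filters alone produced 20% v 15% (assumed), a useless DCP would be significant 36% of the time at 300 per group.

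**The case against.** The plan is openly a non-randomized pilot cohort. Its hypothesis is worded as an association, it names eligible non-participants as a comparator, and it collects their EMR characteristics and reasons for declining. All of that stands. What remains is that no method is given for the non-participant comparison, no analysis keeps decliners with accepters, and no sensitivity analysis for unmeasured confounding is planned.

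Starting the controls' window at an office visit gives them an opportunity for an LDCT order, which may offset some of the bias. That also stands, and its size is unknown.

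Four stronger readings are tempting and not supported:
- *The payment drives the bias.* The $50 is for participation, not for a scan, and could equally attract less motivated patients. Its direction is unknown; the consent step is what creates the selection.
- *Controls were certainly never approached.* Data Acquisition pulls lists from both practice types and does not expressly limit physician review and letters to participating practices. It simply describes no contact or consent for controls.
- *Selection could explain the whole planned 30 points.* Acceptance alone is capped at 15 points. Reaching 45% v 15% would need selection at reach as well (q = 0.25) and a ratio of about nine: 0.25·45% + 0.75·5% = 15%. Nothing in the documents supports that ratio.
- *An offer-based comparison would settle the question.* It removes selection at acceptance but not at reach or confirmed eligibility.

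**Conclusion.** The point holds as a limit on what Aim 1 can conclude. The asymmetry at consent is documented, and the specified matching variables reduce it only as far as they happen to predict willingness. At a 15% background, a useless DCP would be declared different about 9% to 43% of the time with 100 pairs, and 11% to 59% with 150, for assumed volunteer rates of 18% to 25%; the nominal rate is 5%. At a background near 4% the inflation is smaller. These figures rest on an assumed accepter-to-decliner ratio, 50% acceptance, a two-sided 5% test, and no offset from the controls' office-visit start. They show that a positive result could arise without a DCP effect, not that it will.

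**What to change.** Keep the matched comparison as primary. In Statistical analysis, Aim 1, state that it estimates an association among volunteers, and pre-specify three supportive analyses:

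1. LDCT in eligible decliners v matched usual-care controls. A rate clearly below controls signals selection; the absence of a difference does not exclude it, given the power shown above.
2. Everyone on the EMR lists, as extracted and before physician removals, at participating v non-participating practices, adjusted for the same EMR variables. Report this as the effect of the whole outreach programme. Do not divide by uptake without a caveat, because letters and physician list review may themselves act on non-participants.
3. Accepters plus decliners v matched controls, labeled as still selected on reach and phone-confirmed eligibility, and not used alone to support a causal reading.

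Decliners and unreached patients have no counseling session from which to count 60 days. Define one index-date rule for participants, decliners, unreached patients and controls in these analyses, such as a common calendar or list date, or an office-visit date.

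**Cost.** SAP wording, plus an EMR pull of LDCT for decliners and unreached patients, since the items listed for them do not include it; confirm that the ethics approval covers this. The list-wide effect is diluted to about 2.3 points, with about 49% power at a 15% background and 90% at 4%, so none of these analyses replaces the primary one.

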Specific Aims

In 2013, the United States Preventive Task Force (USPSTF) recommended use of annual low dose CT scans (LDCT) to screen high-risk individuals for lung cancer. This recommendation was based on evidence that detecting and treating early-stage lung cancer would greatly lower the risk of dying from this disease. Unfortunately, lung cancer screening rates in the United States are very low— just 3.3% in 2010 and 3.9% in 2015 (1). **Not yet known** is how to effectively promote and increase lung cancer screening while supporting patients and physicians in making this high stakes decision. There is a critical need to develop and implement effective strategies to engage high risk patients, those who have a substantial history of smoking, in a coordinated program of lung cancer screening which includes shared-decision making.

The **long term goal** of this work is to decrease lung cancer mortality through primary care interventions. Such interventions should leverage the patient-physician relationship and support patients to make informed decisions about lung cancer screening that is aligned with current medical evidence and emphasizes patient values and preferences. In 2017, our research team took an initial step to towards achieving this goal by assessing the feasibility of implementing an informed decision making intervention in a single primary care practice among 54 patients who were eligible for lung cancer screening. The intervention centered the Decision Counseling Program ® (DCP)(2) an online software application that focuses on patient education and preference clarification related to lung cancer screening delivered over the phone by a trained nurse educator. DCP results were given to patients and providers. Use of the DCP intervention was feasible, helped primary care patients clarify their preference related to screening, and participants were likely to undergo LDCT screening. We now propose to **modify and expand the intervention**. We will recruit 100 eligible, current smokers from real world primary care practices to participate in a pilot study, outlined in **Figure 1** comparing to usual care by propensity scoring.

[figure not shown]
Aim 1 Compare low dose CT scan completion in the DCP cohort of current smokers versus usual care, propensity-matched controls at 60 days.

Aim 2 Compare the characteristics of the patients not recruited in the study to the characteristics of those who accepted to enroll

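### DCP patients are confirmed eligible by contact, but usual-care controls are only picked from EMR lists, so the primary comparison can be biased in either direction

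*Combined protocol and SAP*

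**What the plan says.** Under Data Acquisition, both groups start from the same kind of source: "lists of potentially eligible individuals from participating and non-participating practices will be obtained from EMR data". PCPs may then "review lists and eliminate any patient they feel would not be appropriate for this study".

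The paths then separate:

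- **DCP group.** "After an opt-out period of 7 working days, patients will be contacted, screened for eligibility and invited to participate". The criteria under Study population/eligibility are age 55-80, a 30 pack-year history, "no symptoms consistent with cancer, and no CT scan of the lungs within the last year".
- **Control group.** "Eligible patients in the usual care group (in the non-participating clinics) will be identified electronically as stated above". Neither contact nor chart confirmation is described.

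The EMR items said to be available for everyone, controls included, are demographics, insurance, marital status, smoking status, comorbidities and zip code. Pack-years appear only as an addition for people who are reached: "Information collected from individuals who are reached but ineligible will include all of the above plus smoking status, pack years, and reason for ineligibility". Under Statistical analysis, Aim 1, the propensity model is built "using all the patients level variables extracted from the medical records as listed above", and a simple chi-square then compares LDCT completion within 60 days.

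The Aim 1 hypothesis also names a second comparator, eligible people who do not take part. Aim 2 describes the characteristics of those who refused, but no LDCT comparison with non-participants is planned.

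**The concern.** A check that most reached patients are expected to fail is applied to one group only. Three of the items it covers (pack-years, symptoms, recent lung CT) are not among the listed matching variables. The matched groups could look well balanced on every listed characteristic and still differ in the share who qualify for screening.

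The bias can go either way:

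- Ineligible controls may have fewer screening LDCTs, which is plausible for those with low pack-years. The control rate then falls, and the test can favour DCP when DCP does nothing.
- A control with a lung CT in the last year is also ineligible. Specific Aims notes that the USPSTF "recommended use of annual low dose CT scans (LDCT) to screen high-risk individuals for lung cancer", so a repeat scan may fall inside the 60-day window and raise the control rate.

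The documents do not give the mix of reasons for ineligibility. The planned analysis cannot show how much of an observed difference comes from eligibility, and the Sustainability section presents the work as groundwork for a randomised trial.

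**Working it through.** **Inputs from the plan**

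- Expected yield of the phone screen: 300 of 1000 reached = 30% (Power calculation).
- Pilot yield: 54/297 = 18% overall, 28% in current smokers (Preliminary Studies).
- Rates: 45% with DCP, 15% in usual care (Power calculation). The text does not say whether the 15% refers to confirmed-eligible or to EMR-listed patients.
- Group sizes: 60 (the plan's figure for a 20-point difference), 100 (recruitment in Specific Aims) and 150 (expected acceptors). Caliper matching may leave fewer.

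**Assumptions.** Alpha and sidedness are not stated; I use 5% two-sided, without continuity correction. The documents give neither q, the eligible share of matched controls, nor r, the LDCT rate in ineligible controls.

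**The plan's own figures.** For 15% vs 45% with 40 per group, the normal approximation gives 84.7% power and exact enumeration 85.2%, against the stated 85%. The recruitment chain also reproduces: 2000 × 0.5 = 1000; × 0.30 = 300; × 0.50 = 150.

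**Reading A: eligible patients screen at 15%, and DCP has no effect.** The control rate is c = 0.15q + (1 − q)r, so the spurious gap is (1 − q)(0.15 − r). Rejection rates are from exact binomial enumeration of the chi-square.

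| q | r | Control rate | Gap favouring DCP | Rejection at 60 / 100 / 150 pairs |
|---|---|---|---|---|
| 70% | 5% | 12.0% | 3 points | 7% / 10% / 12% |
| 50% | 5% | 10.0% | 5 points | 13% / 19% / 26% |
| 30% | 5% | 8.0% | 7 points | 22% / 35% / 48% |
| 30% | 0% | 4.5% | 10.5 points | 51% / 74% / 89% |
| 30% | 15% | 15.0% | 0 | 5% / 5% / 5% |
| 30% | 20% | 18.5% | −3.5 points | 8% / 10% / 13% |

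In the zero-gap row, half of the rejections favour DCP. In the last row nearly all go against it.

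**Reading B: 15% is the rate among all EMR-listed usual-care patients.** The rate in eligible patients is then (0.15 − (1 − q)r)/q.

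- q = 50%, r = 5%: (0.15 − 0.025)/0.5 = 25%. The gap is 10 points, with rejection 28% / 43% / 59%.
- q = 50%, r = 20%: (0.15 − 0.10)/0.5 = 10%. The gap is 5 points against DCP.
- q = 30%, r = 0: 0.15/0.3 = 50%. The gap is 35 points.

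**Tipping share.** With observed control rate c and DCP rate d, eligibility alone explains the whole difference when q is at or below (c − r)/(d − r). With c = 15%:

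| Observed difference | r = 0 | r = 5% | r = 10% |
|---|---|---|---|
| 20 points (35% vs 15%) | 43% | 33% | 20% |
| 30 points (45% vs 15%) | 33% | 25% | 14% |

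With r at 15% or more, no value of q explains either difference.

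**The case against.** The strongest reply is that the variable list governs matching and is not stated to be the filter that builds the control list. The plan calls the controls eligible, sets one set of criteria, and audits LDCT reports in the EMR, so a prior-CT filter could be applied electronically. That is fair: the gap is firmest for pack-years and weakest for prior CT, and the argument for bias against DCP depends on prior CT not being filtered. But the plan does not say that any of these items will be used for controls. PCP review may extend to control practices, yet it judges appropriateness and does not verify pack-years or recent CT.

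On size, the largest illustrations need q = 30% together with r = 0. The 30% describes reached patients in participating practices, and matching on age, smoking status and COPD may raise the eligible share. Under Reading A the bias favouring DCP cannot exceed 15 points, so in expectation it cannot account for all of a 20- or 30-point difference. The tipping shares also imply that eligible usual-care patients complete LDCT at 35% or 45% within 60 days. Specific Aims cites national rates of only 3.3% and 3.9%. If 3.9% applied to eligible patients, q = 30% and r = 0 would give a gap of 3.9 − 1.2 = 2.7 points. All of this stands as a limit on size. It does not remove the bias: even that last case rejects in 11% / 21% / 30% of studies at 60 / 100 / 150 pairs.

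The hypothesis is worded as an association and the study is a pilot. That tempers the claim but does not make the two groups comparable. The missing comparison with non-participants is a separate gap and does not support the main point.

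**Conclusion.** The concern holds and should be fixed. As written, eligibility is confirmed by contact in the DCP group and assumed from EMR lists in the control group, and the listed matching variables cannot be relied on to close the gap. The text shows the asymmetry clearly; the direction and size of the bias are not established. Under Reading A the illustrations run from 3.5 points against DCP to 10.5 points in its favour. They rest on assumed q and r and on a two-sided 5% test. Applying the 30% yield to control practices is a further assumption. There is no bias if matched controls are all eligible, or if ineligible and eligible controls screen at the same rate.

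**What to change.** 1. **Common EMR rule.** Before matching, apply the same EMR-based eligibility rule (pack-years and prior lung CT where recorded) to both groups, at least as a sensitivity analysis, and report data availability by group. Cost: an EMR query in both groups. It can drop controls as well as phone-confirmed DCP patients without recorded pack-years, so fewer pairs remain. DCP patients still pass an extra phone screen, so the asymmetry is reduced but not removed; the SAP should say so.

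2. **Otherwise, labelling.** Describe the controls as potentially eligible and do not attribute the whole difference to DCP. Cost: SAP wording and a more cautious conclusion.

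3. **Two-directional sensitivity table.** Report the eligible-control rate (c − (1 − q)r)/q for q from 30% to 100% and r from 0 to values above c, keeping only results between 0 and 1. With c = 10%, q = 100% gives 10%; q = 50% gives 15% at r = 5% and 5% at r = 15%; q = 30% with r = 0 gives 33%; q = 30% with r = 15% is excluded. Add the tipping share (c − r)/(d − r). The range may be wide. The phone screen's own pass rate and recorded reasons for ineligibility can inform q, on the stated assumption that they carry over to control practices. Cost: a small table.

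4. **Second comparator.** Either delete it from the Aim 1 hypothesis, or define it and add an LDCT comparison as supporting analysis only. That comparison needs the same covariates, a comparable 60-day EMR window and a stated index date, with a note that self-selection may also favour DCP. Cost: one phrase deleted, or an LDCT audit of about 300 − 150 = 150 confirmed-eligible non-participants, after checking that the ethics approval covers it.
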